### 10.4 ECOG PERFORMANCE STATUS

ECOG PERFORMANCE STATUS*	
Grade	ECOG
0	Fully active, able to carry on all pre-disease performance without restriction
1	Restricted in physically strenuous activity but ambulatory and able to carry out work of a light or sedentary nature, e.g., light house work, office work
2	Ambulatory and capable of all selfcare but unable to carry out any work activities. Up and about more than 50% of waking hours
3	Capable of only limited selfcare, confined to bed or chair more than 50% of waking hours
4	Completely disabled. Cannot carry on any selfcare. Totally confined to bed or chair
5	Dead

\* As published in Am. J. Clin. [R01-0787](#)

Proprietary confidential information.

© 2016 Boehringer Ingelheim International GmbH or one or more of its affiliated companies. All rights reserved.  
This document may not - in full or in part - be passed on, reproduced, published or otherwise used without prior written permission.

## 10.5 RECIST (VERSION 1.1)

The criteria below are based on RECIST 1.1 ([R09-0262](#)).

The preferred method of assessment is a spiral CT scan with IV and oral contrast, unless IV and/or oral contrast are medically contraindicated. CT scans of the chest, abdomen and other areas of known or newly suspected disease must be performed. Scans of the abdomen, pelvis and other areas of the body, but not chest, may be done with MRI instead of CT.

Skin lesions followed as target lesions must be documented by colour digital photography and must include in the image a ruler with millimetre subdivisions and a label that includes the patients ID and date.

Bone scans (using  $^{99}\text{m}$ -technetium polyphosphonate scintigraphy) are recommended at baseline if the patient has any signs and symptoms consistent with bone metastasis or a history of bone metastasis. Bone metastasis identified at baseline must be documented and assessed according to RECIST 1.1 at the times of the other tumour measurements indicated in the [flow chart](#). During the study bone scans should be repeated as clinically indicated in patients without bone metastasis at Baseline.

Tumour assessment will be performed every 4 weeks after start of treatment with Kentuzumab (BI 836845) and afatinib for first 8 weeks (prior to courses 2 and 3), in 8-week intervals thereafter (e.g. prior to courses 5, 7, 9, etc.) and in 12-week interval after course 16 until PD or start of further anti-cancer treatment. In the event of a treatment delay, interruption or discontinuation of treatment, tumour assessment should continue to follow the original schedule.

Follow-up tumour assessments must utilize the same CT/MRI/photographic method and acquisition technique (including use or non-use of IV contrast) as were used for screening assessments to ensure comparability. A chest x-ray or skeletal x-ray which clearly demonstrates a new metastatic lesion may be used to document progression in lieu of CT/MRI/bone scan.

### Measurability of tumour at baseline

#### Measurable lesions

Lesions that can be accurately measured in at least one dimension with longest diameter  $\geq 10$  mm (by CT scan, MRI, caliper measurement) or  $\geq 20$  mm (by chest X-ray). Pathological lymph nodes, defined as lymph nodes with a short axis  $>15$  mm are also measurable.

#### Measurable disease

Measurable disease requires the presence of at least one measurable lesion. Measurable lesion if limited to either small ( $<2$ cm) solitary visceral lesion or scant ( $<5$ cm) lymph nodes only

Proprietary confidential information.

© 2016 Boehringer Ingelheim International GmbH or one or more of its affiliated companies. All rights reserved.

This document may not - in full or in part - be passed on, reproduced, published or otherwise used without prior written permission.

metastasis should be evaluated for additional evidence of malignant nature and discussed with BI trial clinical monitor before enrolling.

#### Non-measurable disease

Non-measurable lesions are all other lesions, including small lesions (longest diameter <10 mm with CT scan, MRI or caliper measurement or <20 mm with chest X-ray or pathological lymph nodes with shortest axis ≥10 and <15 mm) as well as truly non-measurable lesions. Lesions considered truly unmeasurable include leptomeningeal disease, ascites, pleural or pericardial effusion, inflammatory breast disease, lymphangitic involvement of skin or lung, abdominal masses/ abdominal organomegaly identified by physical exam that is not measurable by reproducible imaging techniques.

#### New lesions in irradiated fields

Previously irradiated lesions should not be used as indicator lesions unless there has been demonstrated progression in the lesion. However, new lesions occurring in previously irradiated fields can be used to assess the anti-tumour response.

#### **Methods of measurement**

All measurements must be recorded in metric notation, using a ruler or calipers. All baseline evaluations must be performed as close as possible to the treatment start and never more than 4 weeks before the beginning of the treatment. If a lesion is considered too small to measure, a default measurement of 5mm should be applied. If the lesion is not visible, a default measurement of 0mm should be applied.

The same method of assessment and the same technique must be used to characterise each identified and reported lesion at baseline and during follow-up.

Clinical lesions will only be considered measurable when they are superficial (e.g., skin nodules, palpable lymph nodes). In the case of skin lesions, documentation by colour photography including a ruler to estimate the size of the lesion is obligatory.

CT and MRI are the best currently available and reproducible methods to measure target lesions selected for response assessment. Conventional CT and MRI should be performed with cuts of 5 mm or less in slice thickness contiguously. Spiral CT should be performed using a 5 mm contiguous reconstruction algorithm. This applies to the chest, abdomen and pelvis.

Ultrasound, endoscopy and laparoscopy should not be used to measure tumour lesions or evaluate tumour response. However, these techniques can be useful to supplement information from other techniques.

Cytology and histology can be used to differentiate between PR and CR in rare cases (for example, residual lesions in tumour types such as germ cell tumours where known residual benign tumours can remain).

Proprietary confidential information.

© 2016 Boehringer Ingelheim International GmbH or one or more of its affiliated companies. All rights reserved.

This document may not - in full or in part - be passed on, reproduced, published or otherwise used without prior written permission.

## Baseline Documentation of Target and Non-target Lesions

All measurable lesions up to a maximum of two lesions per organ and five lesions in total, representative of all involved organs should be identified as target lesions and will be recorded, measured (longest diameter = LD) and numbered at baseline. Target lesions should be selected on the basis of their size (lesions with the longest diameter) and their suitability for accurate repetitive measurements (either by imaging techniques or clinically). Lymph nodes must be  $\geq 15\text{mm}$  in order to be considered as target lesions.

A sum of the longest diameter (LD) for all target lesions will be calculated and reported as the baseline sum LD. The baseline sum LD will be used as reference to further characterise the objective tumour response of the measurable dimension of the disease (see Table 10.5:1).

Table 10.5: 1 Evaluation of target lesions

Complete Response (CR)	Disappearance of all target lesions.
Partial Response (PR)	At least a 30% decrease in the sum of LD of target lesions taking as reference the baseline sum LD.
Progression (PD)	At least a 20% increase in the sum of LD of target lesions taking as reference the smallest sum LD recorded since the treatment started, together with an absolute increase in the sum of LD of at least 5mm or the appearance of one or more new lesions.
Stable Disease (SD)	Neither sufficient shrinkage to qualify for PR, taking as reference the baseline SoD, nor sufficient increase to qualify for PD taking as reference the smallest SoD since the treatment started.

All other lesions (or sites of disease) should be identified as non-target lesions and should also be recorded at baseline. Measurements are not required and these lesions should be followed as “present” or “absent” (see Table 10.5:2).

Table 10.5: 2 Evaluation of non-target lesions and new lesions

Complete Response (CR)	Disappearance of all non-target lesions and normalisation of tumour marker level. All lymph nodes must be non-pathological in size (<10 mm short axis)
Non-CR/Non-PD	Persistence of one or more non-target lesions or/and maintenance of tumour marker level above normal limits.
Progression (PD)	Appearance of one or more new lesions and/or unequivocal progression of existing non-target lesions. Although a clear progression of non-target lesions only is exceptional, in such circumstances, the opinion of the treating physician should prevail and the progression status should be confirmed later by the review panel (or study chair).

In some circumstances it may be difficult to distinguish residual disease from normal tissue. When the evaluation of complete response depends upon this determination, it is recommended that the residual lesion be investigated (fine needle aspirate/biopsy) before confirming the complete response status.

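### Appendix 10.5 classifies lymph nodes by short axis but scores target nodes on longest diameter, so objective response can be misclassified in either direction

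*Protocol*

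**What the plan says.** All of the following is in Protocol Appendix 10.5.

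**Nodes are judged by short axis.** Under Measurable lesions, "Pathological lymph nodes, defined as lymph nodes with a short axis" above 15 mm count as measurable. Under Non-measurable disease, the non-measurable group includes "pathological lymph nodes with shortest axis ≥10 and <15 mm". Table 10.5: 2, the table for non-target lesions, requires for CR that "All lymph nodes must be non-pathological in size (<10 mm short axis").

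**Target lesions are scored by longest diameter.** Under Baseline Documentation of Target and Non-target Lesions, every target lesion "will be recorded, measured (longest diameter = LD) and numbered at baseline", and "A sum of the longest diameter (LD) for all target lesions will be calculated and reported as the baseline sum LD". Neither sentence makes an exception for nodes. In Table 10.5: 1, target CR is "Disappearance of all target lesions" and PR is "At least a 30% decrease in the sum of LD of target lesions taking as reference the baseline sum LD". PD is a rise of at least 20% (and at least 5 mm) over the smallest such sum. The SD row refers instead to SoD, a label found neither in the appendix's definitions nor in the abbreviation lists.

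**The node threshold appears in two forms.** It is above 15 mm short axis under Measurable lesions, and at least 15 mm with no axis named in the text on target lesions.

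**The primary endpoint depends on this text.** Protocol 5.1.1.2 makes objective response (CR or PR) the Part B primary endpoint. Protocol 5.1.2 and SAP 5.1.2 both send the response assessment to Appendix 10.5. The SAP gives no separate rule for nodes.

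**The concern.** The dimension that decides whether a node is diseased or normal is not the dimension that decides whether the patient has responded. A node can shrink across its short axis to a size the appendix calls normal while its longest diameter falls by less than 30%. Because the node is still visible, it has not disappeared either. The patient then qualifies for neither PR nor CR and is counted as a non-responder. A node can also shorten along its length while its short axis changes less, and be counted as PR.

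Two results are exposed. The first is the Part B objective response rate, in a cohort of 18. The second is duration of response: it starts at the first CR or PR and usually ends at PD, and the same sum governs PR and PD. Disease control is not affected by a switch between PR and SD, since both count.

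**Working it through.** **Inputs.** From the documents: PR needs a fall of at least 30% in the sum; a node is normal below 10 mm short axis; a target node is at least 15 mm; Part B has 18 patients; Protocol 7.6 gives a 73% probability of at least 3 responses at a true rate of 20%. The documents give no node sizes and no number of patients with nodal targets, so the lesion sizes and error rates below are assumptions.

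**Step 1. The plan's own figures.** With X binomial (18, 0.20), P(X ≥ 3) = 1 − [P(0) + P(1) + P(2)] = 1 − (0.01801 + 0.08107 + 0.17226) = 0.72866, which is the stated 73%. At a true rate of 25% the result is 0.8647 (stated 86%), and at 1% it is 0.00073 (stated below 0.1%). These figures reproduce and are not in dispute.

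**Step 2. One target node, scored both ways.** Change = (later size − baseline size) / baseline size. Assume no non-target progression, no new lesions, and that the later measurement is confirmed.

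| Case | Short axis x longest diameter, mm | Longest-diameter change | As written | Short-axis change | By short axis |
|---|---|---|---|---|---|
| A | 16 x 30 to 9 x 22 | (22−30)/30 = −26.7% | SD | (9−16)/16 = −43.8%, now below 10 mm | Responder |
| B | 20 x 30 to 13 x 22 | (22−30)/30 = −26.7% | SD | (13−20)/20 = −35.0% | PR |
| C | 20 x 36 to 15 x 25 | (25−36)/36 = −30.6% | PR | (15−20)/20 = −25.0% | SD |

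A and B lose a responder; C gains one.

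**Step 3. A node plus a lung lesion.** The node goes from 18 x 26 to 9 x 20 mm (same order) and the lung lesion from 20 to 16 mm.
- Longest-diameter sum: 26 + 20 = 46 to 20 + 16 = 36 mm; (36−46)/46 = −21.7%, SD.
- Sum with the nodal short axis: 18 + 20 = 38 to 9 + 16 = 25 mm; (25−38)/38 = −34.2%, PR.

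**Step 4. Does the CR wording change objective response on its own?** Suppose the sum used short axes for nodes, all non-nodal targets vanished, and every target node went from at least 15 mm to below 10 mm. Each node would fall by more than 1 − 10/15 = 33.3%, and so would the sum. That patient is at least PR and still counts. The misclassification therefore comes from the longest-diameter sum. The disappearance rule matters only in combination with it: in case A it closes the CR route that would otherwise have kept the patient a responder.

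**Step 5. Size.** One reclassified patient is 1/18 = 5.6 percentage points. For scale only:
- If a fraction f of true responders is missed at a true rate of 20%, the observed rate is 0.20 × (1 − f). P(X ≥ 3) falls from 72.9% to 69.3%, 65.4% or 56.7% for f = 5%, 10% or 20%.
- If a fraction g of non-responders is wrongly counted at a true rate of 1%, the observed rate is 0.01 + 0.99g. P(X ≥ 3) rises from 0.07% to 0.5% or 1.5% for g = 1% or 2%.

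**The case against.** The best defence is that selecting a lesion on one dimension and following it on another is not a contradiction. The measurability text says which nodes qualify, the target-lesion text says how they are summed, and nowhere is the short axis prescribed for the sum. That would hold if the short axis were used only for selection. It is not: the 10 mm limit in Table 10.5: 2 is a response criterion, so the appendix itself uses the short axis to judge whether a node has responded.

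A second defence is that "All lymph nodes must be non-pathological in size" can be read to include target nodes, so that a small residual target node need not block CR. The reading is possible, but the sentence sits in the non-target table, and on that reading it conflicts with the target CR row, "Disappearance of all target lesions". Either way the text needs repair.

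Several objections do stand, against stronger readings that a reader might draw:
- **That the rule lowers the response rate.** Case C goes the other way, and the net direction is unknown.
- **That the CR wording by itself removes responders.** Step 4 shows that it does not, because objective response pools CR and PR.
- **That one patient could decide the trial at 3 of 18.** Protocol 7.2 makes all analyses descriptive with no formal tests, and Protocol 7.6 gives probabilities of observing at least 3 responses without making that number a decision rule.
- **That sites will use different axes.** The appendix describes itself as based on RECIST 1.1, but its wording gives one rule and it requires the same method at baseline and follow-up. Variation between sites is conjecture.
- **That the two threshold wordings matter much.** They differ only for a node of exactly 15 mm.

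It is also fair to say that a correction is more than an edit, because nothing requires nodal short axes to be recorded at follow-up.

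**Conclusion.** The appendix is internally inconsistent for nodal target lesions, and following it as written can give a wrong result on the Part B primary endpoint. A node that becomes normal by the appendix's own limit can leave the patient at SD (case A), and a patient can be scored PR when the nodal dimension has shrunk by only 25% (case C). Duration of response carries the same weakness through PD. The undefined SoD in the SD row adds doubt about which sum applies.

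The size is 5.6 percentage points per affected patient in a cohort of 18. The number affected cannot be derived, since the documents do not say how many patients will have nodal targets; the examples use assumed sizes that straddle the 30% limit, and the error rates in Step 5 are assumptions. The documents support possible error in both directions, not a known bias, and the stated design probabilities remain correct. This should be corrected, but it does not undermine the design.

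**What to change.** In Appendix 10.5, with SAP 5.1.2 following by reference:

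1. Define one target sum: short axis for nodal targets, longest diameter for all others.
2. Use that sum by name in the PR, PD and SD rows of Table 10.5: 1, replacing SoD.
3. For target CR, require non-nodal targets to disappear and target nodes to be below 10 mm short axis, the limit already in Table 10.5: 2.
4. State one node threshold throughout: at least 15 mm short axis.

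The cost is wording plus some re-reading. Baseline short axis is already needed to establish that a node is measurable, but follow-up short axes may have to be checked or measured on existing scans. That includes the Part A patients treated at the RP2D, because SAP sections 7 and 7.4.2 pool them (excluding squamous carcinoma) with Part B for efficacy. The work is limited to target nodes, within the cap of two target lesions per organ and five per patient. The sample size and design do not change.

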## Evaluation of best response to study treatment

The best response to study treatment ([Table 10.5: 3](#)) is the best response recorded from the start of treatment until disease progression or start of further anti-cancer treatment (taking as reference for progressive disease the smallest measurements recorded since the treatment started). In general, the patient's best response assignment will depend on the achievement of both measurements and confirmation criteria ([Table 10.5: 3](#)).

Patients with a global deterioration of health status requiring discontinuation of treatment without objective evidence of disease progression at that time should be reported as “symptomatic deterioration”. Every effort should be made to document the objective progression even after discontinuation of treatment.

Table 10.5: 3 Algorithm for evaluation of overall response\*

Target lesions	Non-target lesions	New lesions	Overall response
CR	CR	No	CR
CR	Non-CR/ Non-PD	No	PR
CR	Not evaluated	No	PR
PR	Non-PD or not evaluated	No	PR
SD	Non-PD or not evaluated	No	SD
Not evaluated	Non-PD	No	NE
PD	Any	Yes or No	PD
Any	PD	Yes or No	PD
Any	Any	Yes	PD

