Subsequent anti-cancer therapy started before progression or death, no more than one consecutively missed radiological assessments prior to start of subsequent anti-cancer therapy	Censored	Date of last radiological assessment before initiation of subsequent anti-cancer therapy

Only radiological assessments after first assessment indicating objective response will be taken into consideration.

Disease control (DC)

DC is defined as best overall response of CR or PR or SD where best overall response is defined according to RECIST version 1.1 (see Appendix 10.5 of the CTP) from first administration of trial medication until the earliest of disease progression, death or last evaluable tumour assessment before start of subsequent anti-cancer therapy.

Note that an adequate tumour assessment includes an assessment of target lesions, as well as radiological tests to evaluate non-target lesions and to search for new lesions, i.e. a RECIST tumour evaluation. If no RECIST tumour evaluation has been performed, the assessment will be set to missing.

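### The written reference for target-lesion progression omits the baseline sum, so growth before the first on-treatment scan is not counted and can end up as disease control

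*Protocol*

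**What the plan says.** Table 10.5: 1 of the protocol (Appendix 10.5) calls target lesions progressed when their summed diameters have risen by 20% or more, "taking as reference the smallest sum LD recorded since the treatment started". The rise must also amount to 5 mm or more in absolute terms, and new lesions count as progression too. The stable-disease row rules out response against the baseline sum but rules out progression differently: "nor sufficient increase to qualify for PD taking as reference the smallest SoD since the treatment started". The text on best response to study treatment repeats the rule: "taking as reference for progressive disease the smallest measurements recorded since the treatment started". Partial response uses another reference: "At least a 30% decrease in the sum of LD of target lesions taking as reference the baseline sum LD".

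Baseline imaging is done before treatment. Appendix 10.5, under methods of measurement, says "never more than 4 weeks before the beginning of the treatment"; Protocol 5.1.2 and SAP 6.7.1 allow 30 days. On-treatment scans fall at weeks 4 and 8 and then every 8 weeks, with a 7-day window (Protocol 5.1.2). Stable disease must be met at an interval of at least 6 weeks (Appendix 10.5, Confirmation).

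SAP 5.2.2.2 states "DC is defined as best overall response of CR or PR or SD". Both that section and SAP 5.1.2 refer to Appendix 10.5 for best overall response. The visible SAP text gives no other reference for progression.

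**The concern.** The sums recorded since treatment started do not include a sum measured before treatment. The table itself treats the two as different things, since the stable-disease row names baseline for shrinkage and the on-treatment minimum for growth. In a patient whose tumour only grows, baseline is the smallest sum, and that is the value the wording leaves out.

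At stake is the Part B disease control rate, a secondary endpoint. It would be shifted upwards in a single-arm cohort with no control group to reveal the shift. Progression dates in the Kaplan-Meier curves planned in Protocol 7.3.2 could also be late. Response is assessed locally by investigators, so sites that read the table differently would record different outcomes from the same measurements. Documented progression also ends treatment (Protocol 3.1 and 3.3.4.1), so the same wording reaches beyond the analysis.

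**Working it through.** There is no stated figure to reproduce, because the issue is a definition. I applied the rule to illustrative sums. All millimetre values are assumptions, as is the absence of new lesions and of non-target progression. The six weeks are counted from the start of treatment.

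**Inputs.** From Table 10.5: 1, progression requires an increase of at least 20% and at least 5 mm over the reference. The minimum for stable disease is 6 weeks = 42 days. Part B has 18 patients (Protocol 7.6).

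**Week 4.** The only sum recorded since treatment started is the week-4 sum itself. The increase over the reference is 0%, so target-lesion progression cannot be met, whatever the baseline was.

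**Week 8.** The written reference is the smaller of the week-4 and week-8 sums. If the tumour grew, that is the week-4 sum.

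| Sums in mm (baseline, week 4, week 8) | Week 8 as written | Week 8 from baseline | As written | Baseline included |
|---|---|---|---|---|
| 50, 64, 76 | 76/64 = 1.188, +18.8% | 76/50 = 1.52, +52% | stable at weeks 4 and 8 | progression at week 4 (64/50 = 1.28, +14 mm) |
| 50, 57.5, 66.1 | 66.1/57.5 = 1.150, +15% | 66.1/50 = 1.322, +32.2% | stable at weeks 4 and 8 | progression at week 8 (+16.1 mm) |

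In the first row the written threshold at week 8 is 1.2 × 64 = 76.8 mm; in the second it is 1.2 × 57.5 = 69.0 mm. With baseline included it is 1.2 × 50 = 60 mm in both.

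**Does it count as disease control?** A week-8 scan at the early edge of its window is at 56 − 7 = 49 days, past 42, so stable disease at week 8 qualifies. A week-4 scan at the late edge is at 28 + 7 = 35 days, so stable disease at week 4 alone does not.

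**What is still caught.** In the first row, suppose week 16 is 90 mm. The smallest on-treatment sum is 64 mm, and 90/64 = 1.406, that is +40.6% and +26 mm: progression as written. With 50, 75, 91 mm, week 8 is 91/75 = 1.213, +21.3%: also progression as written, one scan later than with baseline included.

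**Length of the uncounted stretch.** It runs from the baseline scan to the first on-treatment scan: at most 30 + 28 + 7 = 65 days, or 28 + 28 + 7 = 63 days under the 4-week limit.

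**Objective response.** Partial response uses baseline, so a change needs early growth followed by shrinkage. With 50, 61, 34, 34 mm, the final sums are 34/50 = 0.68 (−32%), a partial response as written. With baseline included, week 4 is 61/50 = 1.22 (+11 mm), which is progression.

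**Size.** Each reclassified patient moves Part B disease control by 1/18 = 5.6 points; two move it by 11.1 and three by 16.7.

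**The case against.** The best defence is that nobody would read the table literally. At the first scan the literal rule compares a sum with itself, so it could never operate. The sentence before the table names the baseline sum as a reference for tumour response, baseline is measured close to the start of treatment, and both documents name RECIST v1.1 as the standard. Investigators may well include baseline from habit.

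That may describe practice at some sites, but it does not cure the wording. The table applies baseline only to partial response and to ruling it out, and the SAP refers to this appendix for its derivations. Using baseline at week 4 solves only part of the problem. From week 8 an on-treatment sum exists and the written reference is that sum. The 50, 57.5, 66.1 mm patient is stable at week 4 on either reading and still differs at week 8.

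The defence is right about scope. Misclassification needs early target growth, then less than 20% further growth by week 8, with no new lesions and no unequivocal non-target progression. The analyses are descriptive, and the primary endpoint is objective response.

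A reader might infer that a tumour could keep growing scan after scan and remain stable throughout. The documents do not support that. The reference is the smallest on-treatment sum, not the previous scan, so it can never rise above the first on-treatment value. A reader might also infer that growth from baseline is the usual pattern in Part B because patients enter with resistant disease. The documents give no figure for it.

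**Conclusion.** The point holds for growth between the baseline scan and the first on-treatment scan. As written, that growth is never counted in target-lesion progression, and a patient 20% or more and 5 mm or more above baseline at week 8 can be scored stable and counted as disease control. The error favours the treatment. Its frequency cannot be derived from the documents; its unit size is 5.6 points per patient among 18.

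Progression dates in the progression-free survival curves may be later for the same reason. The visible SAP text does not set out how progression-free survival is derived, so this part rests on the protocol's definition alone. Severity is moderate: a secondary, descriptive endpoint is affected, and objective response changes only in the unusual sequence of early growth followed by response. The conclusion assumes that the appendix is applied as worded; sites that already include baseline would not produce the error.

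**What to change.** For endpoint derivation, state in the progression row, the stable-disease row and the best-response text of Appendix 10.5 that the reference for progression is the smallest sum on study, including the baseline sum if that is the smallest. Put the same sentence in SAP 5.1.2 and 5.2.2.2. Before database lock, run a programmed check of recorded overall responses against the target-lesion sums in the eCRF, looking at patients whose baseline sum was their smallest.

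Because documented progression also ends treatment, the sponsor must reconcile Protocol 3.1 and 3.3.4.1 with the definition used for the endpoints. How that is settled clinically is for the sponsor and investigators.

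The cost is one sentence in each place and one check on data already collected. Disease control and progression-free survival may look slightly less favourable.
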